13.4.2.7 Degree of Neuropathy

This will be measured by the FACT/GOG-NTX-4 (Version 4)

The secondary scientific objectives include examining the association between the response rate of ABT-888 plus 5FU and oxaliplatin to: 1) Tumors that have decreased expression of or mutations in BRCA-1 or -2; 2) PARP activity levels in serial tumor samples; 3) The expression levels of DNA repair enzymes in tumor tissues; and 4) Pharmacokinetic and pharmacogenomic parameters associated with the metabolism of ABT-888; as well as 5) To isolate and propagate tumor cell lines obtained from patient samples and circulating tumor cells.

13.5 Analysis Plan

The primary and secondary efficacy analyses will be performed on all subjects in the study, except for the secondary efficacy analyses which are being performed in only a subgroup of patients. Subjects who have experienced an adverse event or have received at least one cycle of the study drugs (ABT-888 and 5FU and oxaliplatin) will be included in the safety analysis.

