8.2 Selection of Study Population

This is a multi-institutional study for patients with metastatic pancreatic cancer. Only patients with metastatic pancreatic cancer not amenable for resection will be considered for entry. Subjects must have measurable disease, defined as at least 1 unidimensionally measurable lesion on a CT scan as defined by RECIST.

The target recruitment for this study is 24+48 patients. At the LCCC alone, approximately 150 new cases of pancreatic cancer are seen yearly, at least one-third of which have metastatic disease. Because patients with both untreated (for metastatic disease) and pretreated cancers are eligible, most patients seen in the medical oncology clinic with metastatic disease will be eligible for this trial. As of April 2013, the enrollment criteria were modified to include only patients with a known BRCA-associate genetic mutation OR family history suggestive of a breast or ovarian cancer syndrome (as defined below), which is likely to delay enrollment. However, concurrently, the trial is opening at several centers, which may compensate for the

slower accrual. Therefore, recruitment is anticipated to take 24 – 30 months, and with each patient followed for a minimum of 8 weeks, the anticipated time to complete follow-up of all patients will be 30 – 36 months.

Subjects will undergo screening procedures within 14 days prior to administration of the first dose of ABT-888 on Day 1, unless otherwise specified (though baseline imaging scans must be done within 28 days of Day 1). Adult male and female subjects who meet all the inclusion criteria and who do not meet any of the exclusion criteria will be eligible for enrollment into the study.

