8.2.1 Inclusion Criteria

- 1) Histologically proven pancreatic adenocarcinoma with measurable disease, defined as at least 1 unidimensionally measurable lesion on imaging as defined by RECIST 1.1 criteria.
- 2) A known BRCA-associate genetic mutation OR family history suggesting of a breast or ovarian cancer syndrome, as defined by one or more of the following:
 - Personal or known family history of a deleterious (or indeterminate) mutation in the *BRCA1*, *BRCA2*, *PALBB2*, or one of the *FANC* genes.
 - Personal history of breast cancer and one or more of the following:
 - o Diagnosed \leq 45 years old
 - o Diagnosed at any age with ≥ 1 1st, 2nd, or 3rd degree relative with breast cancer \leq 50 years old and/or ≥ 1 st, 2nd, or 3rd relative with epithelial ovarian cancer at any age
 - o Two primary breast cancer with the first diagnosed at \leq 50 years old
 - o Diagnosed \leq 60 years old with triple negative breast cancer
 - o Diagnosed at any age with ≥ 2 1st, 2nd, or 3rd degree relatives with breast cancer at any age
 - o Diagnosed at any age with ≥ 2 1st, 2nd, or 3rd degree relatives with pancreatic cancer or aggressive prostate cancer (Gleason score ≥ 7) at any age
 - o 1st, 2nd, or 3rd degree male relative with breast cancer
 - o Ashkenazi Jewish descent
 - Personal history of epithelial ovarian cancer
 - Personal history of male breast cancer
 - Personal history of pancreatic cancer and ≥ 2 1st, 2nd, or 3rd degree relatives with breast, epithelial ovarian, pancreatic, or aggressive prostate cancer (Gleason score ≥ 7) at any age
- 3) Age ≥ 18 years
- 4) ECOG performance status 0-2 (See Table 2, Below)
- 5) Subjects with no brain metastases or a history of previously treated brain metastases who:
 - Have been treated by surgery or stereotactic radiosurgery (SRS) at least 4 weeks prior to enrollment
 - AND have a baseline MRI that shows no evidence of active intracranial disease
 - AND have not had treatment with steroids *for brain metastases* within 1 week of study enrollment
- 6) Prior therapies:
 - a. For patients stratified to the untreated arm:
 - i. Untreated patients should have received zero prior therapies for metastatic disease.
 - ii. They may have received prior adjuvant chemotherapy and/or radiation therapy, but not within 6 months prior to treatment.
 - iii. They may have received prior *palliative* radiation therapy for unresectable disease, but without any systemic chemotherapy, even as a radiosensitizer

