13.0 STATISTICAL CONSIDERATIONS

13.1 Objectives

The primary objective of the phase I portion of this study is to establish the recommended phase II dose. The primary objective of the phase II study is to determine the objective response rate (CR+PR) of ABT-888 combined with 5FU and oxaliplatin in patients with metastatic pancreatic cancer, stratified by prior therapy. Secondary clinical objectives include determining the disease control rate, progression free survival, overall survival, time to disease progression, duration of disease control, and tolerability and safety of the combination of ABT-888 and 5FU and oxaliplatin.

The secondary scientific objectives include examining the association between response to ABT-888 plus 5FU and oxaliplatin to: 1) Tumors that have decreased expression of or mutations in BRCA-1 or -2; 2) PARP activity levels in serial tumor samples; 3) The expression levels of DNA repair enzymes in tumor tissues; and 4) Pharmacokinetic and pharmacogenomic parameters associated with the metabolism of ABT-888; as well as 5) To isolate and propagate tumor cell lines obtained from patient samples and circulating tumor cells.

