of the 9 patients achieve an objective response with ABT-888 plus 5FU and oxaliplatin, the combination will be rejected and the trial stopped. However, if at least 1 patient of the 9 (11%) exhibits response in the first stage, then an additional 15 patients will be entered into the second stage, for a total of 24 patients in this phase II study. If 3 (12%) or more patients exhibit response, then the treatment will be considered for further investigation. *Because of the change in the inclusion criteria prior to initiating Phase II, patients enrolled in the Phase I portion of the study at the phase II dose will not be included in the efficacy assessment as part of the Simon Two Stage design.*

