13.5.1 Efficacy Endpoints

13.5.1.1 Primary Efficacy Endpoint: Objective Response Rate

The objective response rate will be computed for all subjects with at least one measurable lesion at baseline.

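### The safety set depends on having had an adverse event, and the primary ORR set is not limited to Phase II or to a stratum

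*Combined protocol and SAP*

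**What the plan says.** **Safety set.** Section 13.5 puts a subject in the safety analysis on either of two grounds: having had an adverse event, or having received at least one cycle of the study drugs. Section 13.5.4.3 counts events with onset from the day of the first dose. Section 11.1 defines the study drugs as ABT-888, 5FU and oxaliplatin.

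**ORR set.** Section 13.5 states: "The primary and secondary efficacy analyses will be performed on all subjects in the study", with an exception only for secondary analyses done in a subgroup. Section 13.5.1.1 adds: "The objective response rate will be computed for all subjects with at least one measurable lesion at baseline". Measurable disease is already inclusion criterion 1 in 8.2.1 ("Histologically proven pancreatic adenocarcinoma with measurable disease"), so this filter removes no eligible patient. On the size of the study, 8.2 says: "The target recruitment for this study is 24+48 patients".

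**The Phase II question.** Section 8.1 gives Phase I the recommended dose as its primary endpoint and gives ORR to Phase II. Section 13.1 sets the Phase II objective as the ORR "in patients with metastatic pancreatic cancer, stratified by prior therapy". Section 8.2 records that, as of April 2013, "the enrollment criteria were modified to include only patients with a known BRCA-associate genetic mutation" or a suggestive family history. Section 13.2 gives this as a reason, "Because of the change in the inclusion criteria prior to initiating Phase II", and concludes that even Phase I patients treated "at the phase II dose will not be included in the efficacy assessment as part of the Simon Two Stage design".

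**The concern.** The safety rule makes membership depend on the outcome being measured. Patients who stop before completing a cycle stay in if they had an event and fall out if they had none. The denominator loses only event-free patients.

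The ORR rule names neither phase nor stratum. Followed as written, the reported primary estimate would average over several ABT-888 doses, two eligibility definitions and both prior-therapy groups. It would then match neither stratum's Simon decision. Section 13.2's reason for setting aside Phase I patients at the Phase II dose, changed eligibility, applies equally to the reported ORR. For Phase I patients at other doses the dose differs as well. Section 13.5 does not carry that exclusion over.

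**Working it through.** **1. The plan's own design figures.** Inputs from 2.5, 13.2 and 13.3, per stratum: 9 patients in stage 1, stop at 0 responses, 15 more in stage 2, accept at 3 or more of 24; null ORR 5%, target ORR 25%; one-sided alpha 10%, power 90%.

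P(accept | p) = sum over x = 1 to 9 of P(X1 = x; 9, p) × P(X2 ≥ 3 − x; 15, p)

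- p = 5%: 0.093, within the stated 10%.
- p = 25%: 0.903, against the stated 90%.

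The design reproduces. These probabilities involve only the 9 and 24 patients of one stratum, and 13.2 keeps Phase I patients at the Phase II dose out of that count. Neither wording problem enters them.

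**2. Safety set.** Let N be the number treated and k the number treated for less than one cycle with no adverse event. Those k contribute nothing to any numerator, so a true x/N is reported as x/(N − k). The inflation factor is N/(N − k), which is never below 1. The documents do not give k. With N = 48 assumed:

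| k | factor |
|---|---|
| 0 | 48/48 = 1.000 |
| 1 | 48/47 = 1.021 |
| 2 | 48/46 = 1.043 |

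An event seen in 24 of 48 (50.0%) would be reported as 24/47 = 51.1% with k = 1.

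**3. Phase I share of the literal ORR denominator.** Section 13.3 gives Phase I as 3 to 48 patients, estimate 24. Phase II is taken as full: 2 × 24 = 48. The chosen dose, 200 mg twice daily, is cohort 6 in Table 1, and 8.1 enrols cohorts of three. If levels were opened in order with at least three patients each, Phase I had at least 5 × 3 = 15 patients below 200 mg plus 3 at 200 mg, so 18. That rules out the bottom of the 13.3 range.

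| Phase I patients | share = n1/(n1 + 48) |
|---|---|
| 18 (minimum under that assumption) | 18/66 = 27.3% |
| 24 (protocol estimate) | 24/72 = 33.3% |
| 48 (protocol maximum) | 48/96 = 50.0% |

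The 3+3 rules allow at most six patients at a level. So at least 15 of 18, 24 − 6 = 18 of 24, or 48 − 6 = 42 of 48 would have been treated at another dose.

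**4. What the share could do.** Pooled ORR − Phase II ORR = share × (Phase I ORR − Phase II ORR). The documents give no Phase I ORR. For each assumed 10-point difference the pooled figure moves 2.7, 3.3 or 5.0 points (18, 24 or 48 Phase I patients), in either direction.

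**The case against.** The strongest reply is that context already answers the ORR question. Section 8.1 makes ORR the Phase II endpoint, so a primary efficacy analysis exists only there. Section 13.5.4, inside the analysis plan itself, ties the interim analysis and the efficacy cutoff to the Simon design and its ninth patient. Section 2.5 equates a study with a stratum, and 13.2 uses the word for Phase II alone. In 13.5, all subjects is set against biomarker subgroups and the safety set, so it may mean only that every enrolled patient counts. No passage asks for an ORR pooled across phases. On safety, adverse events are defined broadly and collected from first administration, so few treated patients would have neither an event nor a full cycle.

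Much of this stands. Most readers would probably guess Phase II, and the safety effect is probably small. But the ORR answer is inferred, not stated. Section 8.2 uses the same word for all 24+48 patients, the exclusion in 13.2 is confined to the Simon assessment, and 13.5.4 also sends all data available at database lock into the efficacy analyses. An analysis set should not turn on which sense of a word the analyst picks.

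Three stronger readings are tempting and not supported:

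- *Phase I responses count toward the go/no-go decision and inflate its error rate.* Section 13.2 keeps even Phase I patients at the Phase II dose out of it.
- *The plan intends a pooled ORR.* The text is silent on this.
- *The secondary efficacy set contradicts the plan.* The objectives in 7.2.1 are not limited by phase, and 13.2 does not address those endpoints. Naming their population is a clarification, not a correction.

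**Conclusion.** Both points hold as wording faults worth correcting, at moderate weight.

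The safety definition is outcome-dependent as written, and among treated patients its bias runs one way, upward. The size rests on an unknown k. With one or two patients dropped from an assumed 48, percentages rise by a factor of 1.021 or 1.043.

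The ORR set is under-specified. Under the literal reading about a third of the denominator (24/72) would be Phase I patients. The share is at least 18/66 = 27% if levels were opened in order with three patients each, and up to 48/96 = 50%, with Phase II full at 48. Most of these patients would be at other doses, under the earlier eligibility. Whether the reported ORR would rise or fall, and by how much, cannot be known from the documents. The Simon decision keeps its acceptance probabilities of 0.093 at 5% and 0.903 at 25%. What is at stake is the reported estimate, not the decision.

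**What to change.** - **Safety set (13.5).** Define it as all patients who received any dose of any study drug, using the 11.1 definition. Report Phase I by dose level and Phase II separately.
- **ORR set (13.5 and 13.5.1.1).** State that ORR is computed in Phase II patients, by prior-therapy stratum, on the same patients used for that stratum's Simon decision, with a cross-reference to 13.2. List Phase I response separately by dose level.
- **Secondary efficacy endpoints.** Add a sentence naming the population, as a clarification.

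The cost is wording and a few more tables, with no new patients or data. Per-stratum estimates are less precise. Section 13.5.1.1 specifies no interval for ORR, but if an exact 95% interval is given, an observed 25% yields 9.8% to 46.7% with 6/24, against 13.6% to 39.6% with 12/48 (both strata) and 15.5% to 36.6% with 18/72 (both phases). The wider interval is the one that belongs to the unit on which each decision is made.

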11.2.5 Selection of Doses in the Study

The standard doses of 5FU and oxaliplatin are part of the modified FOLFOX-6 regimen as detailed above. These are the standard doses used in patients with colon cancer, in particular, but are also used in patients with several other cancer types. These doses will not be compromised, unless the patient experiences toxicities requiring dose reductions.

The starting dose of ABT-888 (40mg) is derived from the Phase 1 trial of ABT-888 in subjects with Non-Hematologic Malignancies (NHM) and Metastatic Melanoma (MM). ABT-888 pharmacokinetic results following the 20 and 40 mg BID doses achieved the steady-state exposures (AUC) that were effective in murine efficacy models. However, newer information available from Abbott, but as yet unpublished states that greater anti-cancer efficacy is seen with higher doses of ABT-888. Thus, the Phase I portion of this trial aims to assess the maximally tolerated dose of ABT-888. The dose of 40mg of ABT-888 is being applied in several other Phase II studies in combination with multiple other chemotherapy regimens.

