13.5.1.2 Secondary Efficacy Endpoints

13.5.1.2.1 Disease Control Rate

The proportion of patients who achieve stable disease (SD) or a partial (PR) or complete (CR) response will be reported with a 95% exact binomial confidence interval.

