13.5.1.2.3 Overall Survival

The overall survival rate will be estimated using Kaplan-Meier methodology and 95% confidence interval will be constructed for the estimated 12-month overall survival rate and for the median.

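### Read literally, section 13.5 estimates efficacy in Phase I and Phase II patients together; the Simon decision is protected, but the secondary endpoints and the reported ORR are not

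*Combined protocol and SAP*

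**What the plan says.** Section 13.5 sets the population for the efficacy analyses: "The primary and secondary efficacy analyses will be performed on all subjects in the study". Its only exception is for secondary analyses that are done in a subgroup. Section 13.5.1.1 adds, for ORR: "The objective response rate will be computed for all subjects with at least one measurable lesion at baseline". Inclusion criterion 1 in section 8.2.1 already requires measurable disease of everyone, so this narrows nothing.

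The study as a whole covers both phases. Section 8.2 states: "The target recruitment for this study is 24+48 patients". Section 8.1 gives the same sum as the most that will be enrolled, and section 13.3 gives 24 as the estimate for Phase I.

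The two phases recruit differently. Section 8.2 records: "As of April 2013, the enrollment criteria were modified to include only patients with a known BRCA-associate genetic mutation OR family history". Section 13.2 places that change before the start of Phase II and, for that reason, says that Phase I patients treated at the Phase II dose "will not be included in the efficacy assessment as part of the Simon Two Stage design".

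The secondary endpoints carry no restriction of their own. DCR "will be reported with a 95% exact binomial confidence interval". For OS, a "95% confidence interval will be constructed for the estimated 12-month overall survival rate and for the median". Sections 13.5.1.2.1 to 13.5.1.2.5 do not mention phase, dose or stratum.

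**The concern.** The sponsor saw that Phase I patients do not belong with the selected Phase II population and said so, but only for the Simon count. The same reason applies to every other efficacy estimate, and for those the only population rule is the first sentence of 13.5.

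At stake are the figures that would describe the regimen and plan the next trial: DCR with its interval, and median and 12-month PFS and OS. Taken literally, they would describe a mixture of starting doses and two eligibility rules, not 200 mg BID in the selected population. The reported ORR could also rest on up to 72 patients while the decision rests on 24 per stratum. Because the wording allows two denominators, the choice could be made after the data are seen.

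**Working it through.** **1. The decision rule.** Inputs from sections 2.5, 13.2 and 13.3: 9 patients per stratum, stop at 0 responses; 24 in total, go at 3 or more; response rates of 5% and 25%.

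P(go | p) = Σ over x = 1 to 9 of P(Bin(9, p) = x) × P(Bin(15, p) ≥ 3 − x).

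- At 5%: 0.093, within the stated 0.10.
- At 25%: 0.903, matching the stated 90%.

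The plan's figures reproduce. Section 13.2 keeps Phase I out of this count, so nothing below alters them.

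**2. The Phase I share under the literal reading.** Inputs: 24 Phase I patients (planning estimate) and 48 Phase II patients (maximum, two strata of 24).

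- Planned: 24/72 = 33%.
- One stratum stops at stage 1: 24/(24 + 33) = 42%.
- Both stop: 24/(24 + 18) = 57%.
- With 18 Phase I patients, the fewest that reach 200 mg (six levels, 40 to 200 mg, × 3): 18/66 = 27%.

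**3. Starting doses.** Section 8.1 expands a cohort to at most 6. At most 6 of 24 Phase I patients could have started at 200 mg, so at least 24 − 6 = 18 (75%) started at another dose.

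**4. Effect on DCR.** The documents give no DCR for either phase. Assume 50% in Phase II and a Phase I rate lower by a gap d.

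Pooled rate = [24 × (0.50 − d) + 48 × 0.50]/72.

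The exact (Clopper-Pearson) 95% interval from 72 patients contains 0.50 when the pooled count is 28 to 44. Coverage is the probability that Bin(24, 0.50 − d) + Bin(48, 0.50) falls in that range.

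| Gap d | Pooled DCR | Coverage of the Phase II rate |
|---|---|---|
| 0 | 50.0% | 95.6% |
| 5 points | 48.3% | 94.7% |
| 10 points | 46.7% | 92.2% |
| 20 points | 43.3% | 81.4% |
| 30 points | 40.0% | 62.6% |

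For Phase II alone (n = 48, counts 17 to 31) coverage is 97.1%. With 18 Phase I patients and a 20-point gap it is 89.1%. A Phase I rate higher by the same amount gives the same coverage at 50%, with the bias upward.

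**5. Effect on the reported ORR.** Assume 25% in Phase II, the design alternative. For Phase I take the 5FU-oxaliplatin range in section 13.3, 2.5% to 23%, as an assumption.

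- Low end: (24 × 0.025 + 48 × 0.25)/72 = 17.5%.
- High end: (24 × 0.23 + 48 × 0.25)/72 = 24.3%.
- With the 27% from one first-line trial in section 5.6: (24 × 0.27 + 48 × 0.25)/72 = 25.7%.

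The shift can be large, negligible or slightly upward.

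**The case against.** The strongest reply is that pooling was never intended. The document uses the word study at several levels: for the whole trial, for the Phase II part (13.1, 13.2), for a single stratum (2.5) and for the dose escalation. ORR is tied to Phase II in sections 7.1.2, 8.1 and 13.1, and section 13.5.4 sets the efficacy cutoff by the ninth patient, which is Simon stage 1. Section 13.2 excludes only Phase I patients at the Phase II dose, which suggests that the others were never candidates. This stands as a plausible reading, most of all for ORR. It does not settle DCR, PFS, OS, time to progression or duration of disease control: neither their objectives in 7.2.1 nor their analyses in 13.5.1.2 are limited to Phase II.

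A second reply is that nobody knows whether the phases differ. That also stands. A reader might infer that the plan itself predicts worse Phase I outcomes, because section 11.2.5 says "greater anti-cancer efficacy is seen with higher doses of ABT-888" and section 12.3.3 expects BRCA-deficient patients among the responders. The documents do not go that far. The dose statement rests on unpublished company information, and the same section says that 20 and 40 mg reached exposures that were effective in mice. Section 12.3.3 concerns molecularly defined deficiency, while Phase II also admits indeterminate mutations and family history alone. Section 5.2 suggests that the strategy may also work in BRCA-proficient tumours.

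A third reply is that no test or threshold depends on the secondary endpoints. That is true, and it limits the severity.

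**Conclusion.** The point holds as a population rule that, read literally, gives the wrong denominator for the secondary efficacy endpoints and possibly for the reported ORR. About 24 of 72 patients (33%) would come from a phase with different eligibility, and at least 18 of them from other starting doses. These counts are planning figures; actual enrolment is not given.

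The size of the bias rests wholly on assumed differences between the phases. For DCR, coverage of the Phase II rate falls from about 96% with no gap to 95% at 5 points, which is negligible, and to 81% at 20 points and 63% at 30, which is not.

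Two stronger readings should be resisted. A reader might infer that the go/no-go decision is contaminated; section 13.2 prevents that, and the design's error rates are as stated. A reader might also take the Phase I upper limit of 48 in section 13.3 and conclude that Phase I could equal a full Phase II; section 8.1 caps enrolment at 24 + 48, so that case lies outside the plan.

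**What to change.** Reword the first sentence of 13.5, and 13.5.1.1 to match: ORR and all secondary efficacy endpoints are estimated in all enrolled Phase II patients (200 mg BID). Keep the rule in 13.4.1 and 13.4.2.1 that patients lost to follow-up without a valid response assessment count as non-responders. Report each stratum alongside the Phase II total. Report Phase I efficacy separately and descriptively, by starting dose.

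This takes two sentences and needs no new data, no more patients and no change to the dose or the Simon design. The price is precision. At an observed DCR of 50%, the exact 95% interval is 38 to 62% with 72 patients (36/72), 35 to 65% with 48 (24/48) and 29 to 71% within a stratum (12/24). If Phase II only was always meant, the edit simply says so.
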